3.3 Hypothesis

Two ports plus one puncture laparoscopic cholecystectomy (TPPOP LC) is as safe and effective as conventional laparoscopic cholecystectomy (CLC).

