1.3 Justification

Cholecystectomy is one of the most common elective operations in No.(1) Military Hospital (700 bedded) Pyin Oo Lwin. In 2018, 145 cholecystectomies were done (1/700 MH OT-Registry, 2018). Almost all cholecystectomies were done by conventional laparoscopic technique. Laparoscopic cholecystectomy has rapidly replaced open cholecystectomy as a standard treatment of symptomatic gall stones.

Conventional laparoscopic cholecystectomy is still gold standard procedure, but it still has chance of complications like wound infection, pain, bleeding and injury to nearby structures such as bile duct, bowel or liver. Among these injuries, bile duct injury is common and the percentage is 1% to 2%. The rate of open conversion from CLC is less than 1% (Sreenivas et al, 2016).

Two ports plus one puncture laparoscopic cholecystectomy is also acceptable procedure but it can carry longer operation. The percentage of bile duct injury is 1% to 3%. The conversion rate to conventional procedure is about 5.45% and to open procedure is about 0.18% (Sreenivas et al, 2016). Recent studies demonstrated two ports laparoscopic cholecystectomy using 2.3 mm alligator grasper has acceptable outcome. The main advantages of this two ports LC can be performed safely, principle as the previous conventional technique, reduce number of port, less painful, better for specimen delivery, higher cosmesis with shorter hospital stay (Nasir et al, 2018). Two ports laparoscopic cholecystectomy using conventional umbilical and epigastric ports assisted by 2.3mm alligator grasper may be the method of choice when considering laparoscopic cholecystectomy on a day-case basis due to early recovery.

Therefore, the key question about two ports plus one puncture laparoscopic cholecystectomy (TPPOP LC) is whether it provides a significant advantage over conventional laparoscopic cholecystectomy technique (CLC) now in use. There is no such comparative study in Military Hospitals and Myanmar yet.

So this study will compare the outcomes between conventional laparoscopic cholecystectomy (CLC) and two ports plus one puncture laparoscopic cholecystectomy (TPPOP LC). It may also help to find out safe and effective treatment options for symptomatic gallstones patients.

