4.5 Sample size determination

Target population of this study is patients with symptomatic gall stones requiring laparoscopic cholecystectomy and it will be carried out in surgical wards of No. (1) Military Hospital (700 bedded). The minimal required sample size can be calculated as follow;

$$n = \frac{(Z_{1-\alpha/2} + Z_{1-\beta})^2 (\sigma_1^2 + \sigma_2^2)}{(\mu_1 - \mu_2)^2} \quad (\text{Lwanga S.K. \& Lemeshow S., 1993})$$

n= minimum required sample size

For 95% confidence level, $Z_{1-\alpha/2} = 1.96$ (for two sided)

For power 80%, $Z_{1-\beta} = 0.84$

$\mu_1 = 2.85$ (Analgesic need after CLC) (Sreenivas et al, 2016)

$\mu_2 = 2.31$ (Analgesic need after TPPOP LC) (Sreenivas et al, 2016)

$\sigma_1 = 0.79$

$\sigma_2 = 1.02$

n = 44

After adding 10% drop out

$n_1 = 49$

The minimum required sample size will be 49 in each group, 98 in total.

By receiving the hospital statistics, patients who was treated by laparoscopic cholecystectomy were about 150 patients a year in No.(1) Military Hospital (700 bedded) Pyin Oo Lwin. So the require sample size can be met within the study period.

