4.10 Data analysis

Data will be recorded by using a pre-structured proforma. Data will be collected as categorical as well as numerical variables. Record files will be constructed in Microsoft Excel. The base line data will be entered into data base file. The final data file in Microsoft Excel will be exported as data base file. The categorical data will be calculated by appropriate statistical method such as Chi-square. For continuous variables, the statistical significance of patients will be analyzed by two independent Student's t test. The level of significance will be set at $P < 0.05$. After data analysis, the result will be presented in dummy tables and figures.

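### The hypothesis is a no-worse claim without a margin, but the sizing and the tests are for a difference, so the plan has no valid route to it

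*Protocol*

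**What the plan says.** - **Section 3.3 (Hypothesis):** "Two ports plus one puncture laparoscopic cholecystectomy (TPPOP LC) is as safe and effective as conventional laparoscopic cholecystectomy (CLC"). No margin or other criterion for this appears anywhere in the protocol.
- **Section 4.5 (Sample size):** a two-sided comparison of mean analgesic need at 95% confidence and 80% power. The CLC mean is 2.85, the mean labelled "Analgesic need after TPPOP LC" is 2.31, and the SDs are 0.79 and 1.02. The result is 44 per arm, or 49 after 10% dropout. No safety outcome is sized.
- **Section 4.10 (Data analysis):** "The categorical data will be calculated by appropriate statistical method such as Chi-square". For continuous outcomes, "the statistical significance of patients will be analyzed by two independent Student's t test". "The level of significance will be set at" P < 0.05.
- **Dummy tables 4, 7 and 13** (intraoperative complications, conversion to open, postoperative complications): counts, percentages and a P value.
- **Section 1.3 (Justification):** the key question about TPPOP LC "is whether it provides a significant advantage over conventional laparoscopic cholecystectomy technique (CLC) now in use". Bile duct injury is put at 1% to 2% for CLC. For TPPOP LC, "The percentage of bile duct injury is 1% to 3"%.
- **Sections 3.1 and 3.2:** the aim and all four objectives are worded as comparisons. Analgesic requirement, on which the trial is sized, is not among the objectives.

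**The concern.** A test of no difference can reject equality but cannot establish it. To conclude that one technique is as safe as another, the plan must say how much worse would still be acceptable and then show that the data exclude anything beyond that. This protocol does neither, and its sample size comes from a different question on a different outcome.

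Safety is where this matters most. The injuries of interest are rare and the arms are small, so a non-significant P value is the expected result whether or not TPPOP LC carries more risk. Set beside the hypothesis in 3.3, such a result could be mistaken for support, although it would say almost nothing about relative safety.

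**Working it through.** **1. The plan's own sample size.** Inputs are from section 4.5.

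n = (1.96 + 0.84)² × (0.79² + 1.02²) / (2.85 − 2.31)² = 7.84 × 1.6645 / 0.2916 = 44.75 per arm.

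This rounds up to 45. The stated 44 is truncated, and 44 / 0.9 gives 49. The difference of one patient does not matter here. The figure reproduces as a test of a difference: power for a true difference of 0.54 is 79% at 44 per arm and 83% at 49.

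**2. What that size can detect on safety.** Inputs: 49 per arm and the bile duct injury ranges in 1.3. Method: exact enumeration of all binomial outcomes, counting those with two-sided P < 0.05.

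With no injuries under CLC, the uncorrected chi-square test first reaches P < 0.05 at 4 injuries under TPPOP LC (P = 0.041) and Fisher's test at 6 (P = 0.027). At true rates of 1% and 3%:
- P(0 under CLC) = 0.99⁴⁹ = 0.611.
- P(4 or more under TPPOP LC) = 0.059. The product is 0.036, which is nearly all of the chi-square power.
- P(6 or more under TPPOP LC) = 0.0034. The product is 0.0021, which is nearly all of the Fisher power.

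| True rates, CLC v TPPOP LC | Fisher | Uncorrected chi-square |
|---|---|---|
| 1% v 3% (widest contrast within the ranges in 1.3) | 0.2% | 3.7% |
| 2% v 3% | 0.1% | 2.7% |
| 1% v 2% | 0.03% | 1.1% |
| 1.5% v 6% (6% is an assumption, not a protocol figure) | 3.7% | 18.9% |
| 4.76% v 9.52% (overall rate in 1.2; the doubling is an assumption) | 5.6% | 16.7% |

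At 44 evaluable per arm the first row falls to 0.1% and 2.8%.

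**3. What a clean result would show.** With 0/49 in each arm, the Wilson upper limit is z² / (n + z²) = 3.84 / 52.84 = 0.0727. The Newcombe 95% interval for the difference is therefore −7.3 to +7.3 points. At 44 per arm it is ±8.0 points. With 0 v 3 injuries in 49, P is 0.08 (chi-square) or 0.24 (Fisher), while the interval runs from −2.2 to +16.5 points. That result is not significant, yet it is compatible with a large excess.

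**4. What margin the size could support.** The protocol gives none, so I solved for it at one-sided 0.025, 80% power, equal true rates and 44 evaluable per arm:

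margin = (1.96 + 0.84) × √(2p(1 − p) / 44)

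- p = 2%: 2.8 × 0.0298 = 8.4 points.
- p = 4.76%: 2.8 × 0.0454 = 12.7 points.

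The normal approximation is rough at such low counts. In the other direction, at a 2% rate a 5-point margin needs 124 evaluable per arm, a 3-point margin 342 and a 2-point margin 770. For mean analgesic need, a margin equal to the whole assumed effect (0.54) needs 45 per arm and half of it (0.27) needs 180.

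**The case against.** Several points on the other side have force.

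- **The aim and objectives only promise comparison.** Two-sided tests of difference serve that. The defect lies in the one-sentence hypothesis and its mismatch with the sizing, not in the whole design. This stands, and it keeps the repair small.
- **A reader might infer that the investigators will take P ≥ 0.05 as proof of equal safety.** The protocol never says so. What it supports is narrower: a test of difference is the only criterion it plans, and that cannot establish the hypothesis. Nor is the non-significance rate for one injury type the rate at which the trial would declare TPPOP LC as safe, since safety here also covers bowel, vascular and nearby-structure injury, wound infection and ileus.
- **A reader might build the case on a 6% injury rate with TPPOP LC.** The protocol gives 1% to 3%, so 6% is only an assumption. The case does not need it, because power is lower still at the protocol's own figures.
- **A reader might count the question in 1.3 as a third, separate aim.** It is background text, and it points the same way as the superiority sizing in 4.5. There are two framings, not three.
- **Intervals and test details may sit in an analysis plan.** Chi-square is named in 4.10 only as an example, so Fisher's test is not excluded, and missing intervals alone would be no finding. However, an analysis plan cannot make 44 evaluable per arm adequate for a tight no-worse claim. The hypothesis and the sizing are both fixed in the protocol, and they conflict.

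**Conclusion.** The concern holds as a contradiction within the protocol. Section 3.3 makes a no-worse claim with no margin, while 4.5 and 4.10 plan for and test a difference, so no result under the plan can validly establish the hypothesis. On bile duct injury, the widest contrast that the protocol's ranges allow (1% v 3%) would reach P < 0.05 in 0.2% to 3.7% of trials with 49 per arm, and two injury-free arms would leave about ±7.3 points of uncertainty. These figures assume 49 analysed per arm, independent patients and the rates in 1.3, and they worsen slightly at 44. The margin range of about 8 to 13 points assumes complication rates of 2% to 4.76%, equal in both arms. How a non-significant result would in fact be reported is not stated, and this conclusion does not depend on it.

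**What to change.** 1. **Section 3.3:** restate the hypothesis as the question the sizing supports, a difference (superiority of TPPOP LC) in postoperative rescue-analgesic requirement.
2. **Sections 3.2, 4.5, 4.9 and Table 12:** add that outcome to the objectives and use one unit throughout. At present 4.5 gives no unit, 4.9 lists milligrams and Table 12 tabulates doses. Confirm that the means and SDs in 4.5 are in the chosen unit.
3. **Section 4.10 and Tables 4, 7 and 13:** report intraoperative injuries, conversion to open and postoperative complications as risk differences with 95% intervals (Newcombe or exact). State that P ≥ 0.05 will not be taken as evidence of equal safety or effectiveness.
4. **If a no-worse claim is kept for any outcome:** name the outcome, set and justify its margin in advance, judge it by the confidence limit, and state what 44 evaluable per arm can support. For complications that is about 8 to 13 points at 80% power. A tighter margin means a larger trial.

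Items 1 to 3 need no extra patients, only consistent wording across several sections and added table columns. The price is a more modest safety conclusion. Whether to take that route or to set a margin and re-size is the investigators' choice.

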4. RESEARCH METHODOLOGY

4.1 Study Design

Hospital based open labeled randomized control study

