[figure not shown]

Figure 24. Metallic clips applied by 5mm clip applier

Step 8. The infundibulum of the gallbladder will be retracted anteriorly by 2.3 mm alligator grasper allowing the gallbladder to be dissected from the liver bed using cautery and blunt or sharp dissection (**Fig 25**).

[figure not shown]

Figure 25. Liver bed after gallbladder dissection

Step 9. Then gallbladder will be placed into a specimen retrieval bag and removed through the 10 mm subumbilical port. This will be removed under vision via video telescope from 5 mm port. If the gallbladder is exceedingly large, full of gallstones, or contains large stones, it may not be possible to safely remove the gallbladder. Options include crushing the stones inside the gallbladder with a clamp, removing many stones/stone fragments to help decompress the gallbladder, and/or enlarging the port incision (**Fig 26 & 27**).

[figure not shown]

Figure 26. Gallbladder placement into a specimen retrieval bag

Figure 27. Gallbladder specimen with multiple gallstones

Step 10. Once the gallbladder is removed, the liver bed will be examined to be sure there is no bleeding or bile leakage.

Step 11. 2.3 mm alligator grasper will be removed and this punctured site will be covered with adhesive plaster only. 10mm subumbilical incision will be closed at the fascial level with non-absorbable sutures. All skin incisions will be closed with non-absorbable sutures.

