4.7.9 Postoperative period

Nasogastric tube will be removed after operation. Antibiotics will be given single dose. If gallbladder perforation with bile spillage is present, antibiotics will be given total three doses.

For postoperative pain control, regular analgesic with paracetamol suppository (750 mg for <50 kg and 1 G for \geq 50 kg body weight of the patient) will be given 6 hourly up to 72 hours. The patient will be assessed the pain score by using visual analogue scale (VAS) within 12 hour, 24 hour, 36 hour and 48 hour. Rescue analgesia will be added with injection of intravenous tramadol 1mg/kg if VAS was more than 4 and/or if the patient suffers breakthrough pain or if the patient complain of pain between the assessments. Total number and dose of rescue analgesia will be recorded in the proforma.

Patient will be discharged according to discharge criteria. The postoperative hospital stay will be calculated and recorded in proforma for each patient. During the hospital stay all cases will be observed daily by the researcher for early postoperative complications till the patients are discharged from the hospital. The complications which will be observed are wound infection, prolonged ileus, bile duct injury and bowel injury. Complications will be diagnosed clinically and confirmed by relevant investigations. These complications will be recorded in the proforma. All the complicated cases will be treated under the experienced consultant surgeon together with the researcher. After resuming oral intake, oral cefixime 200 mg twice a day will be given up to 5th postoperative day. Patient will be ordered to take oral paracetamol 500 mg if they feel pain after discharge.

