Appendix 4: Visual Analogue Scale (VAS)

The postoperative pain will be evaluated according to the VAS (Visual Analog Scale). The VAS consists of a 10 cm line, one end marks with 'no pain' and the other 'the worst imaginable pain'. The patient marks the point on the line to indicate the pain intensity, he or she suffers. The clinician then measures the line from 0 end & scored. Mild pain is 1- 4, moderate pain is 5 – 7 and severe pain is 8- 10 (Sodhi and Fernando 2002).

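### Pain and rescue analgesia depend on what patients report, yet patients are not masked to their operation; partial masking to 48 hours is feasible and would reduce the risk of bias in these outcomes.

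*Protocol*

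**What the plan says.** Section 4.1 describes a "Hospital based open labeled randomized control study". Nothing elsewhere in the protocol masks the patient, the ward staff or the person reading the pain score, and no reason is given for leaving the patient unmasked.

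Pain is self-reported. Appendix 4 states: "The patient marks the point on the line to indicate the pain intensity, he or she suffers"; a clinician then measures the mark. Section 4.7.9 schedules the score "within 12 hour, 24 hour, 36 hour and 48 hour". The same section gives rescue tramadol "if VAS was more than 4 and/or if the patient suffers breakthrough pain or if the patient complain of pain between the assessments", and section 4.8.12 repeats the rule.

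The sample size in section 4.5 rests on one outcome, with a mean of 2.85 for "Analgesic need after CLC" and 2.31 for "Analgesic need after TPPOP LC".

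The wounds differ. Section 4.7.4 uses four trocars for CLC. Section 4.7.5 uses two trocars and a 2.3 mm puncture for TPPOP LC, and at the end "this punctured site will be covered with adhesive plaster only".

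**The concern.** Every trigger for rescue goes through the patient: a score the patient marks, or pain the patient reports. A patient who knows the arm may score or complain differently for that reason alone. The threshold makes this more sensitive. Rescue starts above VAS 4, which is also the boundary between mild (1-4) and moderate (5-7) pain in Appendix 4 and hence in dummy Tables 8 to 11. A small shift in reporting near 4 therefore moves both the pain category and rescue use.

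If analgesic need is rescue use, the outcome that sized the trial is among those exposed. Hospital stay is exposed in part, because one discharge criterion in section 4.8.16 is that oral drugs control the pain.

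Neither a larger sample nor the t test planned in section 4.10 can remove a bias of this kind. It has to be prevented while the data are collected.

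**Working it through.** **1. The plan's own figure.** Inputs from section 4.5: z-values 1.96 and 0.84, means 2.85 and 2.31, SDs 0.79 and 1.02.

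- Sum of variances: 0.79² + 1.02² = 0.6241 + 1.0404 = 1.6645
- Difference: 2.85 − 2.31 = 0.54
- n = (1.96 + 0.84)² × 1.6645 / 0.54² = 7.84 × 1.6645 / 0.2916 = 44.75

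The plan states 44, and 49 after 10% dropout (44/0.9 = 48.9). Rounding up gives 45 and 50. The plan's figures are reproduced to within one patient per group, and that difference does not matter here.

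**2. Precision.** With 44 evaluable per group, SE = √(1.6645/44) = 0.194. The smallest observed difference that reaches p<0.05 is 1.96 × 0.194 = 0.38. With 49 per group, SE = √(1.6645/49) = 0.184.

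**3. Effect of a reporting shift when the operations do not truly differ.** Let b be a difference between arms caused only by knowledge of the arm. The chance of p<0.05 is

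Φ(b/SE − 1.96) + Φ(−b/SE − 1.96).

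The protocol gives no value for b. The values below are assumptions.

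| b (assumed) | b/0.54 | 44 per group | 49 per group |
|---|---|---|---|
| 0 | 0% | 5% | 5% |
| 0.10 | 19% | 8% | 8% |
| 0.135 | 25% | 11% | 11% |
| 0.20 | 37% | 18% | 19% |
| 0.27 | 50% | 28% | 31% |

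Worked row for b = 0.27 and 44 per group: 0.27/0.1945 = 1.39, so Φ(−0.57) + Φ(−3.35) = 0.284. More patients make the problem slightly worse, because the bias stays fixed while the standard error shrinks.

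**4. Can the patient be masked?** Three places in the protocol bear on this.

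- Both operations are done under general anaesthesia (section 4.7.2), so the patient does not see the technique.
- Counselling and consent come before allocation (section 4.7.1), so counselling need not reveal the arm.
- The scores end at 48 hours (section 4.7.9) and so do the rescue intervals in Table 12, so the masking period is short.

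Three other places limit it.

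- Section 4.7.5 puts the puncture under the right costal margin without naming a line, whereas section 4.7.4 fixes the two 5 mm CLC ports on the midclavicular and anterior axillary lines.
- Section 4.7.9 has the researcher observe every patient daily for complications, including wound infection.
- Section 4.7.7 allows conversion to open surgery, which dressings of this kind cannot hide.

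**The case against.** Open label is a declared choice and nothing in the protocol contradicts it. That is true. The point is therefore about a choice that a modest change would improve, not about an error.

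The strongest objections concern size and feasibility, and several of them stand.

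- **Size.** A reader might treat 0.54 as a number of doses and quote a bias as a share of it. Section 4.5 gives no unit. Section 4.9 measures rescue in milligrams, and only Table 12 counts doses. Reading analgesic need as rescue use is natural but not stated. The shifts in the table are assumed.
- **Direction.** A reader might infer that the bias must favour TPPOP LC, since sections 1.2 and 1.3 expect less pain with it. The protocol does not say that patients are told this, so the direction is not established.
- **Masking.** A reader might infer that dressings over the four CLC port sites would mask every patient at almost no cost. The documents do not support this. The puncture may lie away from any CLC port site, one dressing in TPPOP LC would cover intact skin that does not hurt, and wound checks can reveal the arm. The protocol has no cost figures and does not show that ward staff already collect the VAS.
- **Scope.** A reader might infer that no positive result of this trial could be told apart from knowledge of the arm. That goes too far. Operation time, intraoperative injury and conversion do not rest on patient report, and scheduled paracetamol is the same in both arms.

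None of this removes the core: the exposed outcomes include the natural reading of the sizing endpoint, and no attempt is made to mask the patient.

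**Conclusion.** The point holds as a risk of bias confined to pain and rescue analgesia, with partial exposure of hospital stay. It is a worthwhile, low-cost improvement to the design, not proof that the results will be wrong.

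Its size cannot be taken from the documents. Under an assumed reporting shift of 0.10 to 0.27 units, the false-positive rate for the sizing endpoint would be about 8% to 28% instead of 5% with 44 per group, and 8% to 31% with 49. This rests on three assumptions: analgesic need means rescue use, the shift acts as a constant difference between arms, and the SDs of section 4.5 apply. The required sample size does not change. The rescue rule itself is not in question here.

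**What to change.** Before enrolment, amend sections 4.1, 4.7.4 and 4.7.5, with matching text in 4.7.1 and 4.7.9.

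- Do not tell the patient the allocation until after the 48-hour VAS, or at discharge if earlier, and say so at consent.
- Apply the same opaque dressing pattern in every patient, large enough to cover all four CLC port sites and the TPPOP LC puncture wherever it lies under the right costal margin.
- Where existing staffing allows, have the VAS read by someone not told the technique.
- Let wound checks go ahead whenever they are needed, without telling the patient the arm. Record any unmasking in the proforma.
- Treat patients converted to open surgery as unmasked. This is a flag, not a reason to exclude them.
- Describe the trial as patient-masked for pain and rescue only; the surgeon remains unmasked.

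The cost is a few extra dressing materials, a sentence at consent and some change to ward routine. The main drawback is that masking will be imperfect. No endpoint, sample size, drug or operative step changes apart from the final dressing.
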